Importantly, anodal tDCS can modulate linguistic abilities in healthy individuals and improve language performance in patients with post-stroke aphasia, via modulation of effective connectivity in the brain (Fiori et al. 2018). Indeed, anodal tDCS affects structural plasticity in the auditory cortex of normal-hearing and noise-exposed rats (Paciello et al. 2018). These effects are thought to result from enhanced neuroplasticity that can occur as relevant groups of neurons are stimulated to fire together, thereby strengthening neural pathways and improving signal processing. Studies of tDCS and transcranial magnetic stimulation of auditory cortex are limited to normal hearing subjects and have demonstrated several perceptual effects including modulation of the mismatch negativity evoked response potential component, increased temporal resolution, phonetic categorization, and pitch discrimination (see review by (Heimrath et al. 2016)) as well as modulation of the right ear advantage in dichotic listening (Heimrath et al. 2020). However, tDCS has not been studied for enhanced rehabilitation of speech perception in patients with hearing loss.

4) Design & Procedures:

This prospective study involves the completion of a 4 week computer-based auditory training program while administering tDCS. Patients with a unilateral Cochlear Implant will be asked to complete 30-minute sessions of self-directed auditory training while administering tDCS, at least five times per week for 4 weeks. Subjects will be asked to complete daily electronic logs for adverse event reporting and documentation of auditory training compliance. Subjects will be provided with a customized learning and practice plan during the initial baseline visit and given instructions on use of the tDCS device. Subjects will be selected whose sentence recognition scores (AzBio) have plateaued below 65%, which provides an opportunity to detect a measurable improvement in response to the proposed intervention.

The following assessments/procedures will be performed at the MOSCH lab located in the [name]:

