Auditory training methods: Subjects will be provided customized auditory training program using materials from two existing computer-based auditory training programs that can be completed in the home. Specifically, we will use consonant and vowel discrimination and recognition modules from Speech Banana to focus on bottom-up processing tasks. This will allow for practice in discriminating between letters/words (e.g., bat/pat/mat or hid/hood/had). Additionally, modules from the Sound Success program

will be used, which focuses on understanding sentences/conversations in quiet and in noise using different talkers. The latter program also allows the patient to practice listening in familiar contexts (e.g., topics on weather, shopping, and family life). Both programs use an adaptive approach such that the difficulty of training stimuli is adjusted based on performance. Participants will be asked to bring their personal laptop or tablet to the baseline visit (if applicable) so they can download the auditory training software and conduct a practice session before leaving the clinic.

Transcranial Direct Current Stimulation (tDCS): We will use a device that was designed and validated to allow safe and reliable tDCS delivery at home (1x1 tES mini-CT, Soterix Medical, USA). This tDCS system incorporates a customizable headgear for individualized electrode placement and disposable, snap-in electrodes that are easy for the patient to apply at home without assistance. The device also allows the clinical team to control and monitor the home use by the patient. Based on the reports of listening related functional brain imaging (Price 2012), and transcranial stimulation studies (Heimrath et al. 2016), we will deliver anodal stimulation (positive electrode over target) of the primary auditory cortex contralateral to the CI implant.

Patient Reported Outcome Measures will be collected: Speech, Spatial, Qualities of Hearing (SSQ-12), and Cochlear Implant Quality of Life Questionnaire (CIQOL) will be collected at baseline, and the 1 month and 6 month follow-up visits.

An adverse event questionnaire will be collected continuously during the 4 week auditory training sessions and reviewed during each of the weekly tele-visits with a member of the study team.

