Hearing and Speech Evaluation: Hearing thresholds and speech perception performance will be measured during the baseline visit, and 1 month and 6 month follow up visits using standard, validated and standard word and sentence lists presented in quiet and in noise (AzBio Quiet, AzBio +5/+10dB; CNC 50-item list) while the patient is wearing an appropriately programmed CI alone and/or with appropriately fitted contralateral hearing aid (if this is typically worn by the patient).

5) Study Schedule:

Visit 1/Baseline:

Subjects will undergo a screening visit to determine eligibility. The screening visit may be combined with a standard of care visit for patients already being seen for cochlear implant evaluation. Each participant will sign an informed consent before committing to any study-related tests or procedures and will include the following assessments:

- Obtain and document consent from potential participant on informed consent form (ICF).
- Conduct baseline hearing threshold and speech perception testing using standard audiological procedures (e.g., AzBio Quiet, AzBio +5/+10dB; CNC 50-item list) for screening for eligibility and baseline assessment
- Obtain patient reported outcome questionnaires (SSQ-12 and CIQOL)
- Auditory training and assignment of home-based personalized, computer-based rehabilitation/practice plan
- Orientation to tDCS equipment, determination of appropriate stimulation levels and electrode placement

- Conduct integrity evaluation of device using telemetry during initial tDCS trial.
- Repeat subset of speech perception assessment before, during and after the initial tDCS application.
- Instructions for completion of electronic daily diary to record adverse events and compliance of auditory training

The tDCS current will be programmed to 2.5mA prior to the start of integrity testing. If 2.5mA is intolerable, then the current will be reduced to 2.0mA. If a participant is still not able to tolerate 2.0mA, then this will be considered a screen fail and the subject will be removed from study.

Study participants meeting the screening criteria upon completion of the baseline visit will continue on study. Enrolled participants will be given a tDCS device to take home to complete study procedures with instructions to return it at the 1 month post-treatment visit to be completed in person.

Weeks 2-5 (Visits 2 – 5)

During the 30-day treatment period, subjects will be expected to complete the following:

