- Complete daily web-based auditory training with tDCS stimulation for 30-minute sessions, at least five times per week for 4 weeks.
- Completion of a daily diary to record compliance of auditory training with tDCS, as well as to document adverse events that may occur during or after the sessions.
- Video visits will be conducted at least weekly by a member of the research team, starting more frequently in the first week, to provide technical assistance as needed, review reported adverse events, and give reminders regarding completion of the daily diary.

One-Month post-treatment (Visit 6)

Participants will be asked to return at the end of the 30-day treatment period for an in-person visit and undergo the following assessments:

- Hearing threshold and speech perception testing using standard audiological procedures (AzBio Quiet, AzBio +5/+10dB; CNC 50-item list)
- Obtain patient reported outcome questionnaires (SSQ-12 and CIQOL)
- Conduct integrity evaluation of device using telemetry
- Review of adverse events
- Return tDCS device

Six-Month post-treatment (Visit 7)

Participants will be asked to return for an in-person visit and undergo the following assessments:

- Hearing threshold and speech perception using standard audiological procedures (AzBio Quiet, AzBio +5/+10dB; CNC 50-item list)

- Obtain patient reported outcome questionnaires (SSQ-12 and CIQOL)
- Conduct integrity evaluation of device using telemetry
- Review of adverse events since the last visit

Schedule of Events Table							
	Baseline	Week 2 (televisit)	Week 3 (televisit)	Week 4 (televisit)	Week 5 (televisit)	1 month post- assessment (in-office visit)	6 month post - assessment (in-office visit)
	Visit 1	Visit 2	Visit 3	Visit 4	Visit 5	Visit 6	Visit 7
Consent	X						
Hearing and Speech Reception Thresholds	X					X	X
Patient Reported Outcome Measures (SSQ12 and CIQOL)	X					X	X
Auditory Training in office – establish therapy plan	X	X					
In-office tDCS – establish protocol, patient training	X						
Home Auditory training and tDCS (daily)					→		
Weekly video visit to review use & compliance of training		X	X	X	X		
Review of symptoms and adverse events		X	X	X	X	X	X
Subject Compensation	X					X	X

6) **Selection of Subjects:**

Inclusion Criteria

1. Age \geq 18 years of age
2. Patients with a unilateral Cochlear Implant device in use for a minimum of 1 year

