The primary outcome measures of efficacy will be speech perception performance in the best listening condition compared to baseline, progress within the computer-based rehabilitation program and patient report of improved daily communication function. Speech perception performance will be measured using validated and standard word and sentence lists presented in quiet and in noise (AzBio Quiet, AzBio +5/+10dB; CNC 50-item list).

For the primary outcome we are reporting straightforward proportions and will not be conducting any group comparisons. The prevalence with which adverse effects are reported will be determined for the study as a whole and for different time windows during the study. To address efficacy we would compare baseline speech perception and survey results with 1 and 6 month data.

Descriptive analysis will include mean and standard deviations, and may also include evaluate for improvement using paired t-test. Need for statistical consultation is likely to be minimal but will be sought if appropriate.

14) Data & Safety Monitoring:

The PI will ensure proper data and safety monitoring. Any serious adverse events will be reported by the PI to the IRB within 5 business days. Events that are considered both serious and unanticipated will be reported to the IRB within 24 hours of the PI's knowledge of the event. The PI will reconsider study design and procedures in discussion with the IRB should adjustments be warranted.

Adverse events will be monitored from the start of auditory training with tDCS at week 2 until the six-month follow-up visit at visit. The PI and study team will meet frequently to review patient reported adverse events.

The investigator's clinical judgment is used to determine whether a subject is to be removed from treatment due to an adverse event. In the event a subject requests to withdraw from protocol-required therapies or the study due to an adverse event.

Definition of unanticipated and serious adverse events requiring prompt reporting to the IRB are described below:

Unanticipated Problems

The Office for Human Research Protections (OHRP) considers unanticipated problems involving risks to subjects or others to include, in general, any incident, experience, or outcome that meets **all** of the following criteria:

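### Adverse event monitoring starts at week 2 although tDCS is first given at Visit 1, and outcome 7 does not say whether people exposed and then removed that day are counted

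*Combined protocol and SAP*

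**What the plan says.** **First exposure.** Section 5 (Visit 1/Baseline) has an in-office tDCS trial with implant telemetry, and asks staff to "Repeat subset of speech perception assessment before, during and after the initial tDCS application". On tolerability it says: "If 2.5mA is intolerable, then the current will be reduced to 2.0mA". It continues: "If a participant is still not able to tolerate 2.0mA, then this will be considered a screen fail and the subject will be removed".

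**Start of monitoring.** Section 14 says: "Adverse events will be monitored from the start of auditory training with tDCS at week 2". Section 4 says: "An adverse event questionnaire will be collected continuously during the 4 week auditory training sessions". Section 5 places diary completion under Weeks 2-5, where its purpose is "to document adverse events that may occur during or after the sessions". In the Schedule of Events table, the row for reviewing symptoms and adverse events is marked for Visits 2 to 7, and the baseline cell is empty.

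**Text that is open or points the other way.** Section 4 also says, without a start week: "Subjects will be asked to complete daily electronic logs for adverse event reporting and documentation of auditory training compliance". The Visit 1 list in Section 5 includes "Instructions for completion of electronic daily diary to record adverse events and compliance of auditory training". Section 11 has participants report symptoms daily through a REDCap link, again with no start week. Section 13 requires the stimulation and implant sites to be inspected for irritation or tenderness, and the implant checked for abnormal function, after every in-office application. Section 15 has adverse events documented at withdrawal, without saying whether this covers screen fails.

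**The outcome.** Outcome 7 in Section 13 is one of eight listed primary feasibility measures: the share of people with an adverse event of any kind. It gives no denominator. Section 13 also says that adverse effects are measured from the diary, and promises their prevalence overall and by time window.

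**The concern.** Section 2 names safety as part of the first purpose of the study, and Section 11 treats tDCS with a cochlear implant as a new pairing. The first supervised application is where acute symptoms and intolerance would first appear. Section 11 lists headache during or just after stimulation, and lightheadedness as the current ramps up or down.

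If the stated start is followed, those symptoms have no required route into outcome 7. The people most likely to have reacted, those who could not tolerate the current, have been exposed but carry a screen-fail label. Leaving them out would tend to lower the reported proportion. A reader could not tell which base was used, and the first-exposure time window would hold only the examination findings.

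**Working it through.** **1. Does any passage require Visit 1 symptoms to be recorded and counted?**

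| Source | Covers Visit 1? |
|---|---|
| Section 14, monitoring start | No: begins at week 2 |
| Section 4, adverse event questionnaire | No: the 4-week training |
| Section 5, diary completion | Listed under Weeks 2-5; Visit 1 gives instructions only |
| Schedule table, adverse event row | No: six marks, Visits 2-7 |
| Section 4 daily logs; Section 11 REDCap survey | Start not stated |
| Section 5, step-down in current | Needs the participant's report of tolerability; no record of it is named |
| Section 13, examination | Yes, but only skin, tenderness and implant function; no link to outcome 7 stated |
| Section 15, withdrawal | Screen fails not mentioned |

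The text therefore conflicts, and no passage resolves the conflict for symptoms such as headache or lightheadedness.

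**2. The plan's own figure.** Section 7: 10 patients + 4 drop-outs = 14 enrolled at most. This reproduces and is not disputed.

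**3. Weight of one person in outcome 7.** 1/10 = 10.0 points; 1/11 = 9.1; 1/12 = 8.3; 1/14 = 7.1.

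**4. A person who continues.** A missed Visit 1 symptom changes outcome 7 only if that person reports nothing else in at least 5 × 4 = 20 home sessions and follow-up. It is then worth one weight from step 3.

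**5. People removed at Visit 1.** Let x of n continuing people have an adverse event, and let k people be removed after exposure. Neither x nor k is in the documents; the values below are assumptions.

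- Each removed person has a recorded symptom: x/n becomes (x + k)/(n + k), a rise of k(n − x)/[n(n + k)].
- None has a recorded symptom: x/n becomes x/(n + k), a fall of kx/[n(n + k)].

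| Continuing people | k = 1, symptom recorded | k = 2, symptom recorded |
|---|---|---|
| 0/10 = 0% | 1/11 = 9.1% | 2/12 = 16.7% |
| 5/10 = 50.0% | 6/11 = 54.5% | 7/12 = 58.3% |
| 8/10 = 80.0% | 9/11 = 81.8% | 10/12 = 83.3% |
| 10/10 = 100% | 11/11 = 100% | 12/12 = 100% |

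The first row needs ten people with no adverse event in about 10 × 20 = 200 sessions, which is unlikely.

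With no symptom recorded: 5/10 = 50.0% becomes 5/11 = 45.5% or 5/12 = 41.7%.

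If 14 are exposed in all and 2 of them removed with a recorded symptom: 6/12 = 50.0% becomes 8/14 = 57.1%, and 10/12 = 83.3% becomes 12/14 = 85.7%. This takes the 14 to include screen fails. Section 5 suggests that enrolment follows a completed baseline visit, in which case the number exposed could exceed 14.

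**6. Precision.** Exact (Clopper-Pearson) 95% intervals: 5/10, 18.7 to 81.3%; 7/12, 27.7 to 84.8%; 8/10, 44.4 to 97.5%; 10/12, 51.6 to 97.9%. They overlap widely.

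**The case against.** The strongest reply is that this is a small clarification. Purpose (a) concerns administration at home, so a window opening with home training fits it, and a supervised tolerance test that screens people out is a familiar design. Section 14's duty to report serious events to the IRB has no start date, so a serious Visit 1 event is covered. Section 13 speaks of prevalence over the whole study, and its examination requirement follows the outcome list in the same paragraph, so it could be read as feeding outcome 7. Most continuing participants may report some adverse event later anyway. Enlarging the base can even lower the proportion if removed people have nothing recorded. The symptom table that Section 11 mentions, and the start of the home-training arrow in the schedule, are not visible in the text available.

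Much of this limits the size of the problem, and that part stands: the effect may be zero, and Visit 1 is not without a safety check. It does not remove the gap. The reporting duty covers serious events only. The examination would not detect headache or lightheadedness. A reference to the whole study schedules no instrument at Visit 1. The risk of a falsely low proportion from a larger base is real, which is why the denominator should change only together with a Visit 1 survey.

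**Conclusion.** The point holds and should be fixed. Section 14, the questionnaire window and the schedule all start after the first exposure. Outcome 7 has no stated base, and no visible passage brings Visit 1 symptoms into it. The likely direction is downward bias, because intolerance is itself the reason for removal. With 1 or 2 removed people and 5 or 8 of 10 continuing people affected, the difference runs from 1.8 points (80.0 to 81.8%) to 8.3 points (50.0 to 58.3%). All of these counts are assumed, and the documents give no rate of intolerance or of Visit 1 symptoms. The plan states no progression threshold, so no stated decision turns on it. What is lost is the meaning of a listed primary measure and of the promised first-exposure time window.

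**What to change.** 1. In Section 14, start adverse event monitoring at the first tDCS application at Visit 1, and mark Visit 1 in the adverse event row of the schedule. Give the existing symptom survey once after that session, by same-day REDCap link, to everyone who received any current, including those removed that day. State that the answers and the Section 13 examination findings count in outcome 7.
2. In Section 13, define the denominator of outcome 7 as everyone who received any tDCS, Visit 1 included. Count a removed person as having an adverse event only when a symptom or sign was recorded. Report the number removed for intolerance, with reasons, beside the feasibility proportions.

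The current levels, the removal rule, the screen-fail label and the denominators of outcomes 2 and 3 are not touched.

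The cost is one date, one mark in the table, two or three sentences and one extra use of a short survey per person. The reported proportion may rise, or fall slightly if removed people have no recorded symptom.

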3. Sentence recognition scores (AzBio) are below 65% in quiet and/or word recognition scores (CNC) are below 75% in the implanted ear for \geq one year following cochlear implant activation.
4. Ability to access internet to conduct computer-based auditory trainings and weekly video visits with study team weeks 2–5

Exclusion Criteria

1. Non-English speaking
2. Diagnosis (documented or self-reported) of a psychiatric or neurologic condition, or any other comorbidities that may interfere with the study or increase the level of risk (such as dementia, seizures, legal blindness, brain tumor)
3. Implants, other than CI, above collar bone level that may interact with delivery of tDCS
4. Inability to or unwillingness to use electronic devices/computers, participate in video visits, or make required visits

7) **Subject Recruitment and Compensation:**

10 patients from the Duke Head and Neck and Communication Science clinics and/or the Duke Raleigh HNSCS Clinic will be recruited. Patients who meet the inclusion and exclusion criteria listed above will be approached for possible study participation after a member of the clinical care team asks the patient's permission to be contacted by the study team. The study coordinator (or member of the research team) will then review the records, and upon determination that the patient is deemed eligible for this protocol, the clinical research coordinator (CRC) will contact the patient. This may occur in clinic or via phone using an IRB approved phone script. If the patient indicates interest in study participation, the study coordinator will thoroughly explain the required elements of informed consent and all aspects of the study to the subject including inclusion/exclusion criteria, risks, benefits, and alternative to study participation. Up to 14 patients will be enrolled, allowing for 4 drop-outs.

Subjects will be compensated \$75 upon completion of the baseline visit (visit 1), \$100 upon completion of the one-month f/u visit (visit 6) and \$75 upon completion of the six-month follow up visit (visit 7) for total of \$250.

8) **Consent Process:**

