It's possible that tDCS pads may cause damage to hearing aid microphones if they get wet. Therefore, participants who wear a contralateral hearing aid will be instructed to remove it prior to and during the use of tDCS.

Participants will record daily symptoms via a link to a REDCap survey. REDCap will be programmed to alert the PI and/or SC of symptoms with an intensity level reported at 8 or above on the AE/symptom survey, regardless of the duration indicated (refer to table below). The PI, SC, or delegate will contact the patient to obtain additional information and determine if tDCS should be discontinued, and if a referral for medical evaluation is needed.

In conclusion, given the low risk of tDCS and its combination with CI, the risk/benefit is favorable since improvement in the patients’ speech perception due to the administration of tDCS could improve their quality of life.

12) Costs to the Subject:

The study does not involve any costs to subjects. Costs for the audiological assessments will be covered by the study. tDCS devices for in-home use will be provided to study participants at no charge and returned at the end of the 1-month follow-up visit.

13) Data Analysis & Statistical Considerations:

The primary outcome measures of feasibility are: 1) proportion of eligible CI patients who expressed interest in the study; 2) proportion of selected participants who completed tDCS training and demonstrated competence in the office and subsequently at home during remote visits; 3) proportion of participants who completed most or all of the proposed intervention protocol; 4) proportion who completed relevant appointments, and reasons for any missing data; 5) acceptability of patient incentive; 6) patient report of ease/difficulty carrying out the protocol via a patient survey at Visit 2; 7) proportion of people with any adverse events, and 8) other feasibility and acceptability metrics consistent with the latest guidelines on pilot studies (Eldridge et al. 2016). After each in-office tDCS application and at the immediate one month post-intervention Visit 6, the site of tDCS stimulation and the CI site will be visually examined for any skin irritation or tenderness and the internal and external CI devices will be examined for signs of abnormal function. Adverse effects of tDCS will be measured by the intensity and duration of symptoms recorded on the daily diary.

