- unexpected in terms of nature, severity, or frequency given (a) the research procedures that are described in the protocol-related documents, such as the IRB-approved research protocol and informed consent document; and (b) the characteristics of the subject population being studied;
- related or possibly related to participation in the research (possibly related means there is a reasonable possibility that the incident, experience, or outcome may have been caused by the procedures involved in the research); and suggests that the research places subjects or others at a greater risk of harm (including physical, psychological, economic, or social harm) than was previously known or recognized.

Serious Adverse Events

A serious adverse event (SAE) is one that meets one or more of the following criteria:

- Results in death
- Is life-threatening (places the subject at immediate risk of death from the event as it occurred)
- Results in inpatient hospitalization or prolongation of existing hospitalization
- Results in a persistent or significant disability or incapacity
- Results in a congenital anomaly or birth defect

An important medical event that may not result in death, be life threatening, or require hospitalization may be considered an SAE when, based upon appropriate medical judgment, the event may jeopardize the subject and may require medical or surgical intervention to prevent one of the outcomes listed in this definition.

15) Participant Discontinuation or Withdrawal from the study:

Participants will be removed in the event of a serious adverse reaction to tDCS.

Subjects will have the option of withdrawing from the study at any time for any reason. Reason and date for withdrawal, as well as any adverse events since the last study visit will be documented.

The Principal Investigator may discontinue a subject from study treatment, or withdraw a patient from the study. Reasons for study treatment discontinuation or withdrawal may include but are not limited to the following:

- Adverse event or hypersensitivity reactions thought to be related to the tDCS device
- Patient voluntarily decides to withdraw.
- Patient non-compliance with the study protocol.
- Intercurrent disease, which in the opinion of the patient's treating physician, would affect the ability of the patient to continue on the clinical study.
- Patient lost to follow-up.

16) Privacy, Data Storage & Confidentiality:

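### Withdrawal from the study for non-compliance selects the follow-up data on adherence, and no denominator is fixed for the completion and retention proportions

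*Combined protocol and SAP*

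**What the plan says.** **Outcomes (Section 13).** Of the eight primary feasibility measures, four matter here:

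- Outcome 2: "proportion of selected participants who completed tDCS training and demonstrated competence in the office and subsequently at home during remote visits".
- Outcome 3: "proportion of participants who completed most or all of the proposed intervention protocol".
- Outcome 4: "proportion who completed relevant appointments, and reasons for any missing data".
- Outcome 7: the share of people with any adverse event.

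The section promises simple proportions without group comparisons. It names no analysis set, interval or success threshold. For efficacy it compares baseline speech and survey results with those at 1 and 6 months, descriptively and possibly by paired t-test.

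**Withdrawal (Section 15).** "The Principal Investigator may discontinue a subject from study treatment, or withdraw a patient from the study". One open-ended list of reasons serves both acts, and it includes "Patient non-compliance with the study protocol", with no threshold. The reason and date of a withdrawal, and adverse events since the previous visit, are recorded. Nothing is said about attending visits after withdrawal.

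**Numbers (Section 7).** "10 patients from the Duke Head and Neck and Communication Science clinics and/or the Duke Raleigh HNSCS Clinic will be recruited", and later: "Up to 14 patients will be enrolled, allowing for 4 drop-outs".

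**Removal at baseline (Section 5, Visit 1).** A consented person who cannot tolerate the in-office stimulation is classed as a screen failure and removed.

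**The concern.** Failing to carry out the home protocol is both a result the study sets out to measure and a ground for ending participation. The team can see it happening, because Section 4 says the device lets the clinical team monitor home use and Section 5 provides video visits at least weekly. A decision to withdraw someone can therefore be taken with partial knowledge of that person's primary outcome.

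Two things are at stake:

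- **Follow-up data.** Withdrawal from the study, in its ordinary sense, ends the scheduled visits. The speech tests, questionnaires and adverse-event review at Visits 6 and 7 would then be missing for poor adherers, and the comparison with baseline would describe those who adhered.
- **The feasibility proportions.** With no denominator fixed, the same participants can yield different completion and retention figures, depending on whether withdrawn people are counted. A later trial would be planned on those figures.

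**Working it through.** **Inputs.** Target 10 and maximum enrolment 14, with 4 drop-outs allowed (Section 7). Outcomes 2, 3, 4 and 7 as simple proportions (Section 13). The documents give no expected adherence, drop-out rate, effect size or standard deviation, so the number lost and the number completing are assumptions below, shown over a range.

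**Step 1: the plan's own figure.** 10 + 4 = 14, so the stated maximum reproduces. The allowance is 4/14 = 28.6% of those enrolled.

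**Step 2: completion under two denominators.** Let *d* be the number withdrawn or lost, and assume that all 10 others complete. With everyone enrolled in the denominator, completion is 10/(10 + *d*). With the *d* people left out, it is 10/10.

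| *d* | All enrolled | Withdrawn left out | Gap (points) |
|---|---|---|---|
| 0 | 10/10 = 100% | 10/10 = 100% | 0 |
| 1 | 10/11 = 90.9% | 10/10 = 100% | 9.1 |
| 2 | 10/12 = 83.3% | 10/10 = 100% | 16.7 |
| 3 | 10/13 = 76.9% | 10/10 = 100% | 23.1 |
| 4 | 10/14 = 71.4% | 10/10 = 100% | 28.6 |

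Exact (Clopper-Pearson) 95% intervals at *d* = 4 are 41.9 to 91.6% for 10/14 and 69.2 to 100% for 10/10. The lower limit for 10/10 is 0.025^(1/10) = 0.692.

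If only 8 of the 10 retained complete, the figures are 8/14 = 57.1% (28.9 to 82.3%) and 8/10 = 80.0% (44.4 to 97.5%), a gap of 22.9 points. With four lost and ten retained, the gap is largest when all ten complete, so 28.6 points is the worst case within the plan's allowance.

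**Step 3: direction when everyone is counted.** With all enrolled in the denominator and a withdrawal counted as not completed, withdrawing someone cannot raise outcome 3. It can lower it, if that person would otherwise have recovered and finished. Any inflation therefore needs the denominator to shrink.

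**Step 4: the 1- and 6-month comparisons.** A paired comparison uses only people with a follow-up value. Let the mean change be *a* in those retained and *b* in those withdrawn. The mean change over all 14 is (10*a* + 4*b*)/14, so reporting *a* alone is off by *a* − (10*a* + 4*b*)/14 = (4/14)(*a* − *b*) = 0.286(*a* − *b*). With one withdrawn of 11 the factor is 1/11 = 0.091. The documents give nothing from which to estimate *a* − *b*. If poor adherers improve less, the error flatters the intervention. A denominator rule does not repair this, because the missing values stay missing.

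**The case against.** The strongest reply is that both rules are usual. An attrition allowance is ordinary, and so is a discretionary withdrawal clause. A reader might infer three stronger things that the documents do not support:

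- **That these rules by themselves raise the feasibility proportions.** They do not; Step 3 shows that with everyone counted, withdrawal can only lower completion.
- **That drop-outs are replaced one for one and the 10 retained form the denominator.** Section 7 only allows for losses. Outcome 4 asks for reasons for missing data, which would have little purpose if only those retained were counted, and Section 13 gives the prevalence of adverse effects for the whole study. The wording leans towards counting everyone, but does not say so.
- **That low use and symptoms would go unrecorded.** A daily diary, a symptom survey with alerts, device monitoring, weekly video visits and the withdrawal record in Section 15 capture both up to the time of withdrawal.

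It is also fair to say that compliance is not itself a named primary outcome, that outcome 1 (interest among eligible patients) is untouched, and that non-compliance can mean more than missed sessions, so the investigator may have good reason to stop home stimulation.

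All of this stands, and it narrows the point. Two parts remain. Recording why someone left does not set a denominator. Nor does it supply that person's Visit 6 and 7 speech, questionnaire and adverse-event data, although Section 14 intends adverse-event monitoring to run to the six-month visit.

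**Conclusion.** The point holds in a limited form. Section 15 permits, though it does not require, withdrawal from the study on a ground that overlaps primary outcomes 3 and 4. Used before Visit 6, it removes poor adherers from the 1- and 6-month comparisons. This rests on reading withdrawal from the study as ending the visits, which the documents do not contradict. The resulting error is the withdrawn fraction, up to 4/14 within the plan's allowance, times an unknown difference in mean change.

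Separately, the unfixed denominator leaves completion open to being reported as 100% or 71.4% from the same 14 people. That 28.6-point gap assumes that four are lost, all four are left out, and all ten others complete; the documents predict none of these. With one person lost, the gap is 9.1 points.

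Severity is moderate. The study is a single-arm descriptive pilot with no success threshold, a reader given numerators and denominators could recompute the figures, and use, symptoms and withdrawal reasons are already recorded.

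**What to change.** 1. **Section 15.** Separate stopping study treatment from withdrawal from the study. Leave the first to the investigator's judgment, exactly as now. For the second, state that non-compliance with home sessions does not by itself end follow-up: the person stays in the scheduled visits unless they withdraw consent, and counts as a non-completer in outcome 3.
2. **Section 13.** Name all participants enrolled and given tDCS (up to 14) as the denominator for outcomes 2, 3, 4 and 7. For the completion and attendance outcomes, count withdrawals and losses as not completed. A person enrolled to cover a drop-out adds to the denominator and displaces nobody. Report people removed at baseline for intolerance separately and explicitly, so that their place in outcomes 2 and 7 is clear. Give each proportion as a count over its denominator with an exact interval, and label any completers-only figure as such.

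**Cost.** A few sentences, with no added participants or visit types. Completion and retention may look less favourable, and a few visits already planned will be held for low users.
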